5.2.4. Analyses of Categorical Data

The frequency and percentage of subjects in each category will be presented.

5.2.5. Analyses of Time to Event Data

For a subject who experiences the event, the time to event will be the study day corresponding to the actual date of the event or the earliest visit date at which the subject has already experienced the event. For all subjects who have not experienced the event, their time to event will be right censored at the last available measurement time (or visit) used to define whether the subject experienced the associated event.

Time-to-event endpoints will be summarized using the Kaplan-Meier method and estimated survival curves will be displayed graphically. Graphs will describe the number of patients at risk over time. The median and quartiles will be estimated by the Kaplan-Meier method and 95% CIs for the median and quartiles will also be provided.

The log-rank test (stratified using randomization strata) p-value will be used for comparing time to event data between each active group and the placebo group.

5.2.6. Analyses of Tier-1 and Tier-2 Events

Number and percentage of subjects with AEs over the duration of treatment will be provided for each treatment group. Tier-1 and Tier-2 events will be analyzed using methods proposed by Chan and Zhang (1999). Exact methods will be used for Tier-1 events while an asymptotic method will be used for Tier-2 events. Risk differences (each PF-04965842 dose group compared to placebo) and 2-sided 95% CIs will be reported. P-values will be reported only for Tier-1 events.

5.3. Methods to Manage Missing Data

In general, for analyses using descriptive statistics, missing values will not be imputed. In addition, for safety endpoints, missing values will not be imputed. Other methods for handling missing values are discussed below.

5.3.1. Binary Endpoints

For binary endpoints analyzed at each scheduled visit separately, visit windows (see [Appendix 2](#)) will be used to map all observed data into nominal visits. After mapping, for subjects who drop out for any reason or require a rescue medication, any missing data will be defined as “non-responsive” from that point on at all subsequent visits; for other subjects, any observations missing intermittently (including baseline values) will be considered missing completely at random (MCAR) and will remain missing in the analysis.

Additional analyses that are based on statistical considerations will utilize the longitudinal nature of the binary endpoint. A Generalized Linear Mixed Model (GLMM) will be fit to the observed data (i.e., without defining missing data due to dropout as “non-response”). The binary outcome will be modeled using a logistic-normal distribution. Fixed factors will include treatment (PF-04965842 200 mg QD and 100 mg QD and the placebo group), visit (Weeks 2, 4, 8 and 12) and treatment-by-visit interaction. Visit will be modeled as a categorical covariate. A subject-specific random intercept will be used to model the correlation within a subject over time (see [Appendix 3](#)). Missing observations for the active groups will be imputed multiply using a tipping point analysis to estimate the treatment effect under the assumption that the missing data mechanism is missing at random (MAR) or more generally, is missing not at random (MNAR). Using the estimated posterior predictive distribution of the GLMM model parameters obtained using Markov Chain Monte Carlo (MCMC) methods, estimates of the posterior predictive probability of response will be calculated for each treatment group. For subjects with missing data at a visit, the posterior predictive response probability in each PF-04965842 dose group will be re-defined as a weighted linear combination of the posterior predictive response probability from this group and the posterior predictive response probability from the placebo group, where the missing observations in placebo group are assumed to be missing at random (MAR) (see [Appendix 3](#)). These weights are fixed MNAR quantities for the active groups. A single imputation of the missing value will be sampled from a Bernoulli distribution with this corresponding shifted / re-defined probability of response for the PF-04965842 dose groups.

090177e1912f28b6\Approved\Approved On: 26-Jun-2019 09:22 (GMT)

This imputation will be repeated multiple times with different MCMC samples to obtain multiple completed datasets. For each such completed dataset, the estimates of the proportions and CMH-weighted difference of proportions between each PF-04965842 dose group and placebo will be obtained along with the associated standard errors using the methods in [Section 5.2.1](#). Rubin’s rule (Rubin, 1987) will be used to combine the multiple estimates and standard errors across the imputed datasets and provide p-values.

The above analysis can be repeated for different combinations of MNAR quantities which will be applied to the probability of response to assess when the conclusion might change (i.e., tipping). Two important scenarios are included in the tipping point analysis framework. When the MNAR quantities are zero and the posterior predictive probabilities in the PF-04965842 dose groups are not shifted, results are obtained under an assumption of MAR for the missing data mechanism. Alternatively, at the other extreme, when the MNAR quantities are 1.0 for each PF-04965842 dose group, results are obtained under an assumption that the distribution of the missing responses after discontinuation of either dose of PF-04965842 is the same as that of the missing responses on the placebo arm. More detailed descriptions are provided in [Appendix 3](#).

Due to a technical error in the process of transmission and collection of electronic data with the device, the data on the pruritus NRS scale was not collected from several subjects at the scheduled visits of Week 2 (Day 15) and after. This was not restricted to a particular site or country and was not indicative of being related to the missing value of pruritus endpoint or any other endpoints. As such, the missing data mechanism may be reasonably assumed to be missing completely at random or missing at random.

For the binary endpoints derived from the pruritus NRS, a hybrid approach will be used which is partially based on the multiple imputation method described in the previous paragraph. For this analysis, all data missing due to dropouts will be defined as “non-responsive” as described in the first paragraph, but any other data which remains missing at any intermittent visits will be handled using multiple imputation under the MAR assumption (which may be obtained by substituting the MNAR quantities as zero in the analysis described in the previous paragraph; see also, [Appendix 3](#)). At any particular visit, if there are 5 or fewer subjects with missing data in each treatment group after applying the non-responder definition, no imputations will be performed, and the data will remain missing. Note that, as described in the previous paragraphs, the GLMM will be fit to the observed data (i.e., without defining missing data due to dropout as “non-response”).

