Sample size for the study was based on the co-primary endpoints. A sample of 150 subjects randomized to PF-04965842 200 mg QD, 150 subjects randomized to PF-04965842 100 mg QD and 75 subjects randomized to placebo would provide at least 95% power to detect a difference in IGA response rate of at least 20% between PF-04965842 200 mg QD (or PF-04965842 100 mg QD) and placebo, assuming the placebo response rate is 6% at Week 12. Furthermore, this will also provide at least 99% power to detect a difference in EASI-75 response rate of at least 30% between PF-04965842 200 mg QD (or PF-04965842 100 mg QD) and placebo, assuming the placebo response rate is 15% at Week 12.

The Type-I error for testing each individual co-primary endpoint was set at 5%. Since both endpoints are co-primary, the study will meet its primary endpoint only if both hypotheses (corresponding to each co-primary endpoint) are rejected. Therefore, the Type-I error rate remains controlled at 5% for testing the primary endpoints. The power to reject both hypotheses when a true difference exists (alternative hypothesis is true) could be at least 94% depending on the correlation between the endpoints.

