4.1. Full Analysis Set

The Full Analysis Set (FAS) is defined as all subjects who have been randomized and who have received at least one dose of treatment. Subject is assigned to the randomized treatment group regardless of actual treatment received. Analyses for endpoints that are defined based on a threshold of change from baseline (eg, NRS4) will also require the baseline value to be equal to or greater than that threshold (eg, for NRS4, the baseline value needs to be ≥ 4).

It is expected that the FAS as defined here will be identical to an ITT analysis set (randomized and dispensed study medication) because the first dose is administered in-clinic. The number of subjects randomized and dispensed study medication but did not receive treatment will be reported.

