5.2.1. Analyses of Binary Data

Binary data at each scheduled visit will be analyzed by two approaches: (1) the test of hypothesis (and the p-value) between the PF-04965842 treatment groups versus the placebo group will be conducted by the Cochran-Mantel-Haenszel (CMH) statistic adjusting for the effect of randomization strata; p-values from the CMH statistic will be used to establish the superiority of each dose of PF-04965842 to placebo in binary responses; and (2) the proportion of responders in the PF-04965842 treatment groups versus the placebo group will be summarized by the difference and its 95% confidence interval obtained by normal approximation. The difference in proportions will be calculated within each randomization stratum. The final estimate of the difference in proportions will be a weighted average of these stratum-specific estimates using CMH weights. The CMH weight w_k for stratum k ($k = 1, 2, 3, 4$) is given by,

$$w_k = \frac{\frac{n_{ik} n_{ck}}{n_{ik} + n_{ck}}}{\sum_{j=1}^4 \frac{n_{ij} n_{cj}}{n_{ij} + n_{cj}}}$$

where n refers to sample size, the subscript c refers to a comparator group (e.g., placebo) and the subscript i refers to a test group (e.g., either the low or high doses; so that two test statistics are calculated, one for each dose versus placebo). The difference is estimated as $\hat{d} = \sum_{k=1}^4 w_k (\hat{p}_{ik} - \hat{p}_{ck})$, where \hat{p} refers to the estimated relative frequency. An estimate for \hat{p} is obtained as x/n , where x is the number of responders.

Two-sided 95% confidence intervals for the difference (based on a normal approximation) are formed by:

$$\hat{d} \pm 1.96 \sqrt{\sum_{k=1}^4 w_k^2 \left(\frac{\hat{p}_{ik}(1 - \hat{p}_{ik})}{n_{ik}} + \frac{\hat{p}_{ck}(1 - \hat{p}_{ck})}{n_{ck}} \right)}$$

In the above formula for the variance of \hat{d} (under the square-root sign), when the number of responders is zero ($x = 0$), then \hat{p} will be replaced by $0.5/(n + 1)$. This change will be made only for calculating the variance of \hat{d} and not anywhere else. Estimates of the difference in proportions along with the two-sided 95% confidence interval will also be provided for the PF-04965842 200 mg QD group versus the PF-04965842 100 mg QD group. No hypotheses will be tested.

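### Week 12 IGA and EASI-75 values missing without dropout or rescue are assumed MCAR and left out, and no co-primary analysis counts every missing value as non-response

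*SAP*

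**What the plan says.** SAP 4.1 defines the FAS as "all subjects who have been randomized and who have received at least one dose of treatment". SAP 6.1.1 and 6.2.1 make it the population for the primary analyses of Week 12 IGA response and EASI-75, and send the handling of missing data to 5.3.1.

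SAP 5.3.1 has two rules for binary endpoints. After dropout for any reason, or rescue medication, missing values count as non-response from then on. For other subjects, "any observations missing intermittently (including baseline values) will be considered missing completely at random (MCAR) and will remain missing in the analysis". SAP 3.4 softens the baseline part: a missing Day 1 value is replaced by the last earlier observation. Protocol 9.2.3 covers withdrawal from the study only and is silent on values missing for other reasons.

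Support for the co-primaries is a PPAS analysis and a tipping-point analysis in the FAS (SAP 6.1.2, 6.2.2, Appendix 1, Appendix 3). SAP 6.1.2 names EASI-75 where IGA is evidently meant; Appendix 1 does list the tipping-point analysis for IGA.

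NRS4 is treated differently. Values missing without dropout are multiply imputed under MAR, except that at a given visit, "if there are 5 or fewer subjects with missing data in each treatment group after applying the non-responder definition, no imputations will be performed". SAP 6.3.1 adds an FAS sensitivity analysis in which every missing NRS4 value is non-response.

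**The concern.** A subject who is still in the study but has no Week 12 skin assessment leaves the CMH denominator. MCAR says that this absence has nothing to do with treatment or with how the skin is doing. The SAP's only argument of that kind, the device transmission error in 5.3.1, concerns the pruritus NRS. IGA and EASI are rated by an evaluator at the site, so the argument does not carry over.

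Two terms that drive the rule are loose. Week 12 is the last on-treatment visit, so it is unclear what an intermittently missing value means there. The SAP also does not define dropout, while Protocol 6.4 keeps subjects who stop treatment in the study for follow-up. Whether a subject counts as a non-responder or drops out of the analysis can thus depend on how status is coded.

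At stake is a primary estimate whose denominator depends on post-randomisation behaviour. If missing values are related to outcome and unequal between arms, the estimate is biased.

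**Working it through.** **Inputs.** SAP 2.2 gives 150 subjects per active arm and 75 on placebo. It claims "at least 95% power to detect a difference in IGA response rate of at least 20" points, "assuming the placebo response rate is 6% at Week 12", so 26% vs 6%. For EASI-75 it claims "at least 99% power to detect a difference in EASI-75 response rate of at least 30" points over 15%, so 45% vs 15%. Alpha is 5% for each co-primary, taken as two-sided because SAP 5.2.1 uses two-sided 95% intervals. The rate of non-dropout missingness is not given, so every count and rate of missing values below is an assumption.

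**Plan's own figures.** Power = Φ[(d − 1.96·SE0)/SE1], where SE0 is pooled and SE1 unpooled (unstratified approximation).

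- IGA: pooled rate (4.5 + 39)/225 = 0.193; SE0 = 0.0558; SE1 = 0.0451; (0.20 − 0.1095)/0.0451 = 2.01; power 97.8% (96.3% with continuity correction).
- EASI-75: pooled rate (11.25 + 67.5)/225 = 0.35; SE0 = 0.0675; SE1 = 0.0579; power 99.8%.
- Both together: at least 0.95 + 0.99 − 1 = 94%.

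All three stated floors hold and are not in dispute.

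**Three missing per arm, same observed rates.**

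- IGA left out: 26% − 6% = 20.0 points.
- IGA as non-response: 0.26 × 147/150 − 0.06 × 72/75 = 0.2548 − 0.0576 = 19.7 points.
- EASI-75: 30.0 left out; 0.45 × 147/150 − 0.15 × 72/75 = 0.441 − 0.144 = 29.7 as non-response.

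**Equal proportion m missing in both arms.** Left out: rates unchanged, sample sizes multiplied by (1 − m). Non-response: sample sizes unchanged, rates multiplied by (1 − m).

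| m | IGA difference, left out / non-response | IGA power, left out / non-response |
|---|---|---|
| 1% | 20.0 / 19.8 | 97.6% / 97.6% |
| 3% | 20.0 / 19.4 | 97.4% / 97.3% |
| 5% | 20.0 / 19.0 | 97.1% / 96.9% |
| 10% | 20.0 / 18.0 | 96.2% / 95.8% |

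For EASI-75 at 10%, the difference under non-response is 27.0 points and power is 99.4%.

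**Outcome-related, unequal loss.** Hold the planned responders fixed (39 active, 4.5 expected on placebo) and let k active non-responders have no Week 12 value, with none missing on placebo. The difference is 39/(150 − k) − 4.5/75.

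- k = 5: 39/145 − 0.06 = 20.9 points
- k = 8: 39/142 − 0.06 = 21.5 points
- k = 15: 39/135 − 0.06 = 22.9 points

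Counting the missing as non-response returns 20.0 each time. For EASI-75 (67.5 responders), k = 8 gives 67.5/142 − 0.15 = 32.5 points instead of 30.0.

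**Do the planned analyses cover this?**

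- The PPAS requires observed Week 12 IGA and EASI scores (SAP 4.2), so it removes the same subjects.
- The tipping-point analysis imputes every missing response, dropouts included. It therefore replaces the dropout rule as well and does not isolate the effect of the MCAR rule. Placebo values stay at MAR, and the shift stops at jump-to-reference.
- Appendix 1 uses the code NR both for the co-primary analysis, where only dropout and rescue count as non-response, and for the NRS4 analysis in which all missing values do.

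**The case against.** The group affected is narrow. The Week 12 window runs from Day 72 to Day 99 (SAP Appendix 2), so late or unscheduled assessments are picked up. Missing baselines should be rare, since eligibility depends on IGA and EASI at the baseline visit. If the missingness really is MCAR, leaving values out causes no bias and costs little power. Nor is non-response always the stricter rule: in an unstratified z test, 22/145 vs 4/70 gives p = 0.046, while 22/150 vs 4/75 gives p = 0.039. All of this stands, and it keeps the point modest. It does not supply a reason for MCAR, and it leaves the co-primaries without the analysis that NRS4 already has.

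A reader might infer that the FAS primary analysis is a complete-case analysis. It is not: missing data after dropout or rescue stay in as non-response.

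A reader might also infer that the switch at 5 or fewer missing must be deleted, and might size it with the IGA rates. The documents do not support either step. The switch is pre-specified, works visit by visit on counts rather than outcomes, applies only to endpoints from the pruritus NRS, and is backed by the all-non-response analysis in SAP 6.3.1. No NRS4 rates are given from which to size it.

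**Conclusion.** The point holds as a limited one. The primary co-primary analysis combines non-responder imputation for dropout and rescue with available cases for everyone else, on an MCAR assumption that the SAP does not justify for IGA or EASI-75.

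Under benign, equal loss the choice of rule matters little: 0.3 points on IGA at an assumed 3 missing per arm, and 2.0 points at an assumed 10%. Unequal, outcome-related loss could matter more: 1.5 points on IGA and 2.5 on EASI-75 if 8 active non-responders alone were left out. These figures rest on the planned response rates and on assumed counts. The documents do not allow the actual size to be fixed, and they do not show that the rule favours the active arms. The case for change is that the assumption is unsupported and avoidable at small cost.

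**What to change.** In SAP 5.3.1, 6.1.1 and 6.2.1, count any missing Week 12 IGA or EASI-75 response as non-response whatever the reason, so that every FAS subject is in the denominator. Keep the tipping-point analysis, from MAR to jump-to-reference, as sensitivity, and correct the endpoint named in 6.1.2. At minimum, leave the primary rule and add an FAS analysis of both co-primaries with all missing values as non-response, mirroring SAP 6.3.1.

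The cost is a few sentences. Response rates and the difference fall slightly, in proportion to the share missing when that is equal across arms; IGA power stays at 95.8% even at an assumed 10%, above the 95% claimed. SAP 5.3.1 also governs the other binary endpoints, so the text should say whether they follow. The opening of Protocol Section 9 requires an amendment for major changes to the co-primary analyses. The sponsor must decide whether changing the primary rule is one; the minimum option leaves that rule untouched.

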2.2. Study Design

This is a randomized, double-blind, placebo-controlled, parallel-group, Phase 3 study to evaluate the efficacy and safety of PF-04965842 monotherapy in subjects aged 12 years and older with moderate to severe AD and a body weight ≥ 40 kg. The treatment duration is 12 weeks. Subjects will be screened within 28 days prior to the first dose of investigational product to confirm that they meet the subject selection criteria for the study. A total of approximately 375 subjects will be enrolled from approximately 75 sites located globally. A study design schematic is presented in Figure 1.

Figure 1 Study Design Schematic

* At Week 12, eligible subjects may enter a long-term extension study; all other subjects enter the 4 week follow-up period

Qualified subjects completing the 12-week treatment period of the study will have the option to enter a long-term extension (LTE) study B7451015. Subjects discontinuing early from treatment, or who are otherwise ineligible for the LTE study, will undergo a 4-week follow-up period in B7451012.

Subjects who have chronic moderate to severe AD as defined per the inclusion criteria and have a documented history of inadequate response or intolerance to treatment with topical AD medications will be randomized in a 2:2:1 ratio to receive 200 mg PF-04965842 (N=150) or 100 mg PF-04965842 QD (N=150), or matching placebo (N=75) from Day 1. Randomization will be stratified by baseline disease severity (moderate [IGA=3] and severe [IGA=4] AD) and age (age < 18 and ≥ 18 years). Investigators, subjects, and the sponsor study team will be blinded as to treatment group.

A full schedule of activities for the study is provided in [Appendix 9](#).

Study Treatments

- Doses of PF-04965842 will be 200 mg or 100 mg taken QD orally, or matching placebo;

- Treatment duration will be 12 weeks;

Sample Size Determination

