Appendix 3. A Logit-Normal GLMM for Longitudinal Binary Data and Tipping Point Analysis

A Logit-Normal Model

Let Y_{ij} be the binary outcome for subject i ($i = 1, 2, \dots, N$) and visit j ($j = 1, 2, 3, 4$). We assume $Y_{ij} = 1$ for a response and $Y_{ij} = 0$ for a non-response. Then we model as

$$P(Y_{ij} = 1 | x_{ij}, u_i) = \frac{e^{\beta' x_{ij} + u_i}}{1 + e^{\beta' x_{ij} + u_i}} \equiv \pi_{ij}(\beta; u_i)$$

Here, β is a vector of unknown parameters corresponding to the vector of fixed effects x_{ij} and u_i is a subject-specific random effect which is assumed to be normally distributed with mean 0 and variance σ^2 . Note that conditional on u_i , Y_{ij} is independent of Y_{ik} , when $j \neq k$.

The full marginal likelihood of the data is then,

$$L(\beta, \sigma^2) = \prod_{i=1}^N \int_{-\infty}^{\infty} \prod_{j=1}^4 \pi_{ij}(\beta; u_i)^{Y_{ij}} (1 - \pi_{ij}(\beta; u_i))^{(1-Y_{ij})} \times N(u_i; 0, \sigma^2) du_i$$

There is no closed analytical form for this likelihood.

For the present study, the primary endpoint is evaluated at Visit 8 / Week 12 ($j = 4$). There are three treatment groups, so the model term $\beta' x_{ij}$ when written out looks like,

$$\beta_0 + \sum_{k=1}^3 \beta_{1k} \times 1_{(T_i=k)} + \beta_{2j} + \sum_{k=1}^3 \beta_{3jk} \times 1_{(T_i=k)}$$

Here, T_i represents treatment for subject i . The third term in the expression is the effect for visit j and the fourth term in the expression is the interaction effect between treatment and visit. With an overall intercept term, the model is over-parameterized as written and so to fit the model, some restrictions on β are required. The default option (this can be changed using programming syntax) in standard statistical software is to assume $\beta_{13} = 0, \beta_{24} = 0$, thereby interpreting β_{11}, β_{12} as the difference in treatment effect relative to $T = 3$ and $\beta_{21}, \beta_{22}, \beta_{23}$ as the difference in visit effect relative to $V = 4$. Consequently, $\beta_{3jk} = 0$ when $j = 4$ or $k = 3$. So, for example, for a subject taking PF-04965842 100 mg QD at Week 12, the expression would be $\beta_0 + \beta_{11}$. For a subject taking PF-04965842 200 mg QD at Week 12, the expression would be $\beta_0 + \beta_{12}$. For a subject on placebo at Week 12, the expression would be β_0 .

Tipping Point Analysis

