A method to analyze the longitudinal data of a binary endpoint measured during the placebo-controlled period (eg, IGA and EASI-75 response rates at Weeks 2, 4, 8 and 12) under the MNAR assumption is called the tipping point analysis. This tipping point analysis includes

two popular scenarios as special cases: (1) the Jump-to-Reference (JTR) analysis in which the response rate for a missing subject assessment in the active treatment group takes on (ie, jumps to) the rate for the reference or control treatment group and (2) the MAR analysis in which the response rate for a missing subject assessment in each treatment group is based on the posterior predictive response rate for that treatment group alone.

The saturated logit-normal GLMM as described above will be used as the imputation model. Estimation of the model parameters will be performed under the Bayesian framework using Markov Chain Monte Carlo (MCMC) methods. We assign a non-informative prior for each component of β to be independent and identically distributed as $\sim N(0, 10000)$ and assign a weakly informative prior for σ^2 as an Inverse-Gamma distribution with shape=1 and scale=1. With this prior distribution, the 90th percentile for σ^2 is approximately 9.

Let $\beta^b, u_i^b, b = 1, 2, \dots, B$ be a sample from the posterior distribution. A single imputation $\widetilde{Y}_{i,j}^b$ of missing $Y_{i,j}$ is based on the posterior predictive distribution of the response probabilities estimated from the GLMM. For example, if subject i is randomized to PF-04965842 100 mg QD ($T_i = 1$), then at Week 12 ($V = 4$),

$$\text{logit}(\pi_{i,1,4}^b) = \text{logit} \left(P(\widetilde{Y}_{i,4}^b = 1 | T_i = 1, V = 4) \right) = \beta_0^b + \beta_{11}^b + u_i^b.$$

If subject i is randomized to PF-04965842 200 mg QD ($T_i = 2$), then at Week 12 ($V = 4$),

$$\text{logit}(\pi_{i,2,4}^b) = \text{logit} \left(P(\widetilde{Y}_{i,4}^b = 1 | T_i = 2, V = 4) \right) = \beta_0^b + \beta_{12}^b + u_i^b.$$

If subject i is randomized to placebo ($T_i = 3$), then at Week 12 ($V = 4$),

$$\text{logit}(\pi_{i,3,4}^b) = \text{logit} \left(P(\widetilde{Y}_{i,4}^b = 1 | T_i = 3, V = 4) \right) = \beta_0^b + u_i^b.$$

In the tipping analysis, we apply a series of fixed quantities $\delta = (\delta_1, \delta_2)'$ to account for MNAR. We define,

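### The model that imputes missing NRS4 (and IGA and EASI-75 in the supportive tipping-point analysis) omits the randomisation strata and the baseline score

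*SAP*

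**What the plan says.** SAP 5.3.1 lists the terms of the GLMM: "Fixed factors will include treatment (PF-04965842 200 mg QD and 100 mg QD and the placebo group), visit (Weeks 2, 4, 8 and 12"), the treatment-by-visit interaction, and one subject-level term: "A subject-specific random intercept will be used to model the correlation within a subject over time". Appendix 3 writes out the linear predictor with the same terms and states: "The saturated logit-normal GLMM as described above will be used as the imputation model". The model is saturated in treatment by visit only.

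The design and the other analyses use more. In SAP 2.2, "Randomization will be stratified by baseline disease severity (moderate [IGA=3] and severe [IGA=4] AD) and age". The CMH test in SAP 5.2.1 is run "adjusting for the effect of randomization strata", and SAP 5.3.1 applies the CMH-weighted difference to each imputed data set. The MMRM for continuous endpoints (SAP 5.2.3) includes both the stratification factors and the baseline value.

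The GLMM has two uses:

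- **NRS4 (SAP 5.3.1 and 6.3.1).** Dropouts are non-responders. Other missing values are multiply imputed under MAR, and this is the primary analysis at Weeks 2, 4 and 12. The stated reason is a device fault: "the data on the pruritus NRS scale was not collected from several subjects at the scheduled visits of Week 2 (Day 15) and after".
- **IGA and EASI-75 (SAP 6.1.2, 6.2.2, Appendix 1).** The GLMM is used only in the tipping-point analysis, which is labelled supportive. The bullet in 6.1.2 names EASI-75, but Appendix 1 lists the tipping-point analysis for IGA as well.

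**The concern.** Response depends mechanically on the baseline score. NRS4 is analysed in subjects with baseline NRS of at least 4. A subject at 4 must reach 0, while a subject at 10 need only reach 6. An IGA responder must end at 0 or 1, a fall of at least 2 points from IGA 3 but at least 3 points from IGA 4. The imputation model sees none of this unless it comes through outcomes observed after baseline.

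MAR is always conditional on what the model contains. Here that is arm, visit and observed responses. If missingness also relates to severity or baseline itch, the imputed values are drawn from the wrong mix of subjects, and the later stratified analysis cannot repair that. Week 2 NRS4 for 200 mg is tested at 2.5%, and its result decides whether Sequence A is tested at 5% or 2.5%. The imputation model therefore feeds an alpha-controlled test.

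**Working it through.** **1. The plan's own figure.** The power statements do not involve the GLMM. The only stated figure that does is the prior for the random-intercept variance: Inverse-Gamma(1,1), with a 90th percentile of approximately 9 (Appendix 3). Its distribution function is exp(-1/x), so the 90th percentile is -1/ln(0.9) = 9.49. This agrees.

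**2. What the model imputes at delta = 0.** With no post-baseline data the likelihood says nothing about u, so u is drawn from N(0, sigma²). The predictive probability is the integral of expit(eta + u) over that distribution, where eta depends only on arm and visit. Taking sigma² = 4 and eta = -1 at every visit (assumed for illustration):

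| Observed so far | Predicted response |
|---|---|
| nothing | 0.352 |
| one non-response | 0.217 |
| one response | 0.601 |
| two non-responses | 0.159 |
| two responses | 0.718 |

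Each value is the same for IGA 3 or 4, for any age and for any baseline score. One observed visit individualises only in part. For delta above 0, an active-arm subject gets a mixture with the placebo probability, and at delta = 1 the placebo probability itself.

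**3. Bias in the treatment difference.** None of these inputs is in the documents except the 150 and 75 per arm. Assumed: one visit; 40% severe; 20% adolescent with no age effect; baseline NRS about 7 (SD 1.7, limited to 4 to 10); log-odds = -1.7 + 1.6 (active) - 0.8 (severe) + 0.25 per NRS point from 7; 10% or 20% of subjects with no post-baseline data. The simulation used 800 trials per setting, 20 imputations, the CMH-weighted difference and Rubin's rule. The true difference is about 27.5 points. Bias against complete data, in percentage points:

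| Missingness | Arm-only, 10% / 20% | With covariates, 10% / 20% |
|---|---|---|
| completely at random | -0.1 / 0.0 | -0.1 / -0.1 |
| follows severity, same in both arms | +0.2 / +0.3 | -0.1 / -0.2 |
| follows severity, opposite by arm | +0.9 / +1.8 | 0.0 / -0.1 |

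The Monte Carlo error of these figures is 0.06 to 0.11. Average standard errors under the two imputation models differ by at most about 0.13 points.

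**4. Hand check.** The assumptions imply response of 29.6% (severe) and 47.6% (moderate) on active, and 8.1% and 16.2% on placebo. Bias in an arm = missing share × (mean among observed - mean among missing).

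- *Same direction, 10%* (15% of severe and 6.67% of moderate missing). Active: missing mean (0.06×0.296 + 0.04×0.476)/0.10 = 0.368; observed mean (0.34×0.296 + 0.56×0.476)/0.90 = 0.408; bias 0.10×0.040 = 0.40 points. Placebo: 0.10×(0.131 - 0.113) = 0.18 points. Difference: 0.22 points.
- *Opposite direction, 10%* (active 17.5% / 5%, placebo 2.5% / 15% for severe / moderate). Active: 0.10×(0.410 - 0.350) = 0.60. Placebo: 0.10×(0.127 - 0.154) = -0.27. Difference: 0.87 points.

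These match the simulation. At 20% the same formula gives 0.90 - 0.41 = 0.49 and 1.35 + 0.61 = 1.96. Both are slightly above the simulated 0.3 and 1.8, by amounts up to about twice the simulation error of 0.10.

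**The case against.** The strongest reply has four parts.

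- **Few subjects may have no data.** NRS was recorded daily from Day 1 to Day 15, and the Week 2 window in SAP Appendix 2 runs from Day 2 to Day 22. A subject who lost Day 15 and everything later can still have a Week 2 value from an earlier diary entry. NRS4 dropouts are not imputed, and nothing is imputed at a visit where every arm has 5 or fewer missing. This stands. The documents give no count.
- **The SAP argues that the loss was technical.** It says the loss was not confined to a site or country and showed no sign of relating to pruritus. If so, bias is about zero. This stands as far as it goes, but the SAP settles on MCAR or MAR and then imputes under MAR, so what the model conditions on still matters.
- **Randomisation is stratified and blinded.** Any link between missingness and severity should therefore be similar across arms and largely cancel in the difference. This is persuasive. Nothing in the documents suggests the opposite-direction setting.
- **There are safeguards.** SAP 6.3.1 plans an NRS4 sensitivity analysis that counts all missing data as non-response and does not use the GLMM.

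Two stronger readings are tempting. A reader might infer that the co-primary results depend on this model. They do not: their primary analyses count dropouts as non-responders (SAP 6.1.1 and 6.2.1). A reader might also take the bias in one arm's rate as bias in the treatment effect. The test is on the difference, where a common mechanism partly cancels, as in step 4 (0.40 less 0.18).

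**Conclusion.** The omission is plain in the text, and no reason is given for it. The imputation model carries less information than the stratified analysis it feeds, and less than the MMRM used for continuous endpoints. It affects the primary NRS4 analysis for missing data other than dropout, and only supportive analyses of IGA and EASI-75.

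The expected consequence is small. Bias is about zero under MCAR. When missingness follows severity alike in both arms it is 0.2 to 0.3 points in simulation, or up to 0.5 by direct calculation. It is 0.9 to 1.8 points (2.0 by direct calculation) only when the direction differs by arm. The simulated standard error of the difference is about 6 points, so none of these settings shows a plausible change of conclusion. All sizes rest on the assumed inputs in step 3 and treat every missing subject as having no post-baseline data; partial data would individualise some imputations. The age term was given no effect, so its contribution is untested. This is a minor improvement that makes MAR more credible.

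**What to change.** Before unblinding, add baseline disease severity, age group and the endpoint's baseline score as fixed effects to the GLMM in SAP 5.3.1 and to the linear predictor in Appendix 3. Use baseline NRS for NRS4 and baseline EASI for EASI-75. For IGA the severity stratum already carries the baseline score, since eligible subjects are IGA 3 or 4. The delta-weighting in Appendix 3 needs no change: each subject's covariate terms enter the active and placebo probabilities alike.

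The cost is two or three further coefficients and no new data. Baseline NRS is complete by construction in the NRS4 population, and baseline EASI is an entry criterion. The one small downside is that the age coefficient may be imprecise if few adolescents enrol, since their enrolment depends on sponsor instruction and local approval. If the model is left as it is, the SAP should say why. It would also help to report, by arm, how many non-dropouts have no post-baseline NRS value.
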